### 1.4 Specific therapy

[figure not shown]
Development of heart failure might be disrupted by specific treatment such CRT where two ventricular PM leads are implanted at two opposite sites. This type of cardiac pacing provides resynchronized electrical activation of the LV. CRT has become one cornerstone of heart failure treatment of patients

with LBBB. According to current guidelines, only patients with established heart failure are being assigned to CRT (39).

Recent studies have focused on predicting response to CRT when heart failure is established (10,16,26,40). Dependent on criteria used for implantation of CRT devices, 30% and 50% are non-responders to CRT (41). This high number indicates either inappropriate patient-selection or irreversibly decreased ventricular function. Based on response defined by echocardiographic measures of volume or ejection fraction modern imaging modalities have been developed in order to predict outcome-prediction for CRT. Additionally, these modalities have shown to be of incremental value for outcome-prediction when a CRT is implanted (26,40).

[figure not shown]
### 1.5 “Novel echocardiographic indices”

Modern echocardiographic modalities like segmental strain imaging allows to visualize and quantify the typical early shortening of the septum followed by the delayed contraction of the lateral wall (10). This pattern has an important prognostic value in patients with established heart failure as its absence was shown to be associated with unfavorable outcome after CRT implantation with increased risk of death or transplantation (40). Computer models could show that the typical strain-patterns changed in dependence on global regional contractility of the septum and lateral wall.

Patients responded to CRT treatment when typical patterns for electro-mechanical dyssynchrony were present. These patterns can be quantitatively assessed by newly developed algorithms (42). In addition to qualitative and quantitative strain-curve analysis “LV workload quantification” and “analysis of energy loss and waste of myocardial work” have been recently introduced as new echocardiographic measures(43) also applicable in the presence of dyssynchrony (12). These are based on strain imaging combined with BP measurements, where strain loop areas can be derived. It has been demonstrated that

contraction of the septum in patients with LBBB and chronic heart failure perform a net negative work (systolic lengthening) while after CRT positive work (systolic shortening) increases dramatically (11). In small patient populations myocardial work showed to be a good indicator for CRT response(44).

**Figure 2:** Pressure strain curves in simulations with narrow QRS complex and with LBBB, and changes with afterload. The area under the curve expresses segmental myocardial work in the septum (upper row) and lateral wall (lower row) (F.Prinzen, E.Willem, J. Lumens JACC-CVI 2019)

## 1.6 Integration of multifaceted data by artificial intelligence

All these new echocardiography-based measures have significantly improved our understanding of the nature of LBBB, its cardio-mechanic effect and the hemodynamic consequences of abnormal electrical activation. Thus, these new measures alone have high potential to improve the selection of adequate treatment strategy. Furthermore, it had been shown that the presence of LBBB morphology on ECG is not always associated with typical mechanical patterns. 30% of patients with LBBB on ECG selected for CRT did not have typical contraction patterns as indicated by speckle tracking strain echocardiography (40). The mismatch between ECG and myocardial mechanics was independently associated with increased risk of adverse outcome. Conversely typical dyssynchrony patterns were observed in 20-26% of patients without typical LBBB morphology at ECG, where the majority responded to CRT (26). All these findings clearly demonstrate that echocardiography may have high potential for accurately selecting patients needing CRT independently of ECG morphology.

As a result of computer-models (38), experimental and clinical studies (36), the interplay of delayed electrical activation, afterload, global and regional myocardial function and the influence on ventricular dyssynchrony or inefficient myocardial work is much better understood. In addition to ECG criteria and

assessment of ejection fraction (EF), echocardiography renders useful information about ventricular loading and function. However, to date CRT management is only based on EF, QRS length, LBBB morphology and NYHA class with a failure rate of still >30% (41). Several echocardiographic studies on CRT response have shown that the failure rate would be expected to be dramatically reduced if imaging would be involved (40,41,45,46).

The development of heart failure and its reversibility is dependent on multiple factors. Unsupervised AI algorithms are recently developed tools being able to integrate individual phenotypic subgroups and identifying isolated characteristics based on strain-curves, echocardiographic phenotypes, flow characteristics, genetics and co-morbidities. A recent important publication has re-analyzed the randomized MADIT CRT study population using AI and were able to identify subgroups with substantially better CRT-outcome in a AI selected patient group with a HR of 0,31 on mortality and adverse cardiovascular events compared to ICD treated patients (9), while the original outcome of the study did not show significant risk reduction by CRT treatment overall.

According to these recent publications, the present study intends to use AI algorithms including evolved echocardiography-based imaging modalities like strain imaging and regional work assessment. We aim to show that these are promising tools to improve assessment of patients with LBBB to identify patients at risk for development of heart failure that might respond to early medical treatment preventing the development of heart failure or identifying patients early who will respond to CRT treatment.

### 1.7 Clinical significance:

LBBB is highly prevalent among patients with chronic heart failure (25%). Morbidity and mortality are high among patients with LBBB, but ECG detected LBBB has not been shown to be a sufficiently accurate predictor of outcome. Early medical treatment or CRT for carefully selected individuals might help to lower morbidity and mortality among individuals with LBBB or PVP. However, criteria for an optimal time-point and patient characteristics for CRT responders are still missing.

In conclusion, the study aims to identify new predictors for the appropriate time point for initiating specific treatment, as well as specific patient characteristics for treatment response based on AI and novel echocardiographic measures. Risk- algorithms for heart failure and increased mortality are

urgently needed in this large group of cardiological patients (25% of heart failure patients). Studies on patients with CRT have demonstrated high specificity of echocardiographic parameters when heart failure is established. Other newer parameters like “septal and lateral work” and as well as integration of all accessible features by AI have been recently introduced and shown to provide a powerful tool for differentiating degrees of dyssynchrony in patients with LBBB. This study aims to contribute to a more specific patient selection for specific heart failure treatment, when LBBB or PVP is present. Patients with His bundle pacing (HBP) might provide synchronous pacing and are also included as a special control-group for patients with permanent ventricular pacing.

## **2 Hypotheses, aims and objectives:**

### **2.1 Primary hypotheses**

1. Typical strain-pattern and myocardial work assessment improve substantially prediction of heart failure development, hospital admission, death and adverse cardiovascular events and can help to establish more effective patient selection criteria for CRT or medical heart failure treatment.
2. AI, incorporating strain imaging and myocardial work assessment as well as conventional clinical patient characteristics is able to improve additionally risk assessment and treatment response in the LBBB population

### **2.2 Secondary hypotheses**

1. Patients with high afterload have typical dyssynchrony patterns with earlier deterioration of cardiac function over time.
2. Repetition of echocardiographic assessment and clinical parameters increases accuracies of outcome-prediction.
3. Predictors for major adverse cardiovascular and cerebrovascular events (MACCE) indicate also CRT- or medical treatment- response. These factors might be useful indicators for risk reduction through treatment of carefully selected patient-groups
4. Patients showing ability to increase or sustain myocardial work during a stress test with no classic pattern of dyssynchrony have a good long-term prognosis.
5. HBP can prevent development of heart failure compared to usual ventricular pacing.

### 2.3 Primary objectives:

1. To identify patients with LBBB eligible for timely CRT treatment by evaluating myocardial work by echocardiography as predictors in for a) deterioration of myocardial function, b) risk for mortality, c) heart failure development and hospital admissions d) risk for MACCE
2. To investigate the ability of AI to improve risk assessment and treatment response in the LBBB population

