## 3 Project arrangements, method selection and analyses

### 3.1 Patients

This is a longitudinal prospective cohort-study intending to include at least 1000 patients with LBBB from University Hospital of North Norway Tromsø and Harstad, Akershus University Hospital, Lørenskog, Oslo University Hospital, Rikshospitalet, Haukeland University Hospital, Bergen and Nordlands Hospital, Bodø, over a 2-year inclusion period.

Information about present and previous diseases, medication, surgical- or invasive treatment, PM, ICD or CRT implantation, clinical examination and present and previous echocardiographic imaging and blood samples (Hb, Thrombocytes, CRP, Kreatinine, eGFR, Urate, HbA1C, Cholesterol, ProBNP, Troponins, ALAT and Ferritin) will be accessed by the patient's journal.

All prospective study participants will answer one customized and two standardized (EQ5D and HeartQoL) questionnaires. They will undergo general clinical investigation comprising height and weight measurements, baseline ECG, blood samples when not found in the patient's journal, standardized BP measurements and echocardiography with a 3 minutes- hand-grip test at baseline and in a 18 month follow-up study.

Clinical outcome data including death and hospital admissions due to heart failure and CRT implantation will be assessed after 3 and 5 years (eventually after 10 and 15 years) by linkage to data from the patient's clinical records through access to Norwegian Patient Registry (Norsk pasientregister (NPR)), Norwegian Causes of Death Registry (Dødsårsaksregisteret) and Norwegian Cardiovascular Disease Registry (Hjerte- og karregisteret).

St Olavs Hospital, Trondheim, might provide retrospective patient data with echocardiography loops, where outcome-data will be extracted from the same registries.

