### 3.11 Statistics

Patients with deteriorating myocardial function will be identified by increasing proBNP by more than 10%, increasing NYHA class, increasing diastolic volume by more than 10% and/or decreasing EF by more than 5%. ANOVA will be used to compare parameters between patients with deteriorating myocardial function and those with unchanged clinical condition after one year. ROC curve analysis will serve to find the ideal cut-off values for continuous variables and assessing sensitivity and specificity of the tests. Univariate and multivariate logistic regression tests will be performed in order to identify the most powerful parameters predicting development of heart-failure with hospital admissions as primary outcome and predicting death (or transplantation) as secondary outcome.

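### Two primary objectives claim CRT eligibility or treatment response, but the analyses stated in the protocol can show only risk

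*Protocol*

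**What the plan says.** **Aims.** Primary objective 1 (Protocol section 2.3) is "To identify patients with LBBB eligible for timely CRT treatment by evaluating myocardial work by echocardiography as predictors" of four outcomes: worsening myocardial function, mortality, heart failure or admission, and MACCE. Primary objective 2 asks whether AI improves both risk assessment and treatment response. Primary hypothesis 1 (section 2.1) says that strain pattern and myocardial work improve prediction and "can help to establish more effective patient selection criteria for CRT or medical heart failure treatment". Primary hypothesis 2 claims better treatment response through AI. Secondary hypothesis 3 (section 2.2) states: "Predictors for major adverse cardiovascular and cerebrovascular events (MACCE) indicate also CRT- or medical treatment- response". Secondary objective 3 (section 2.4) is to compare indicators of risk with indicators of response.

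**Design.** Section 3.1: "This is a longitudinal prospective cohort-study intending to include at least 1000 patients with LBBB". Treatment is not allocated. Section 3.6 enrols patients about to receive CRT and patients who already have it, alongside patients without it. Section 3.5 lists CRT implantation and the start of heart failure medication as secondary outcomes.

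**Analyses.** Section 3.11 gives three. The first is an analysis of variance that sets patients who deteriorate over a year against those who stay unchanged. The second uses ROC curves to choose cut-offs for continuous markers. For the third, the section says: "Univariate and multivariate logistic regression tests will be performed in order to identify the most powerful parameters predicting development of heart-failure with hospital admissions"; a further model takes death or transplantation. Section 3.9 adds unsupervised clustering.

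**The concern.** A marker can predict a poor course without predicting benefit from a treatment. The first is prognosis and can be read from a single cohort. The second is a difference in treatment effect between marker groups, and it needs outcomes with and without treatment within each marker group.

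Primary objective 1 passes from the first to the second in one sentence: eligibility for CRT is to follow from prediction of adverse outcomes. Secondary hypothesis 3 makes the same step, and the AI hypothesis and objective claim response directly. If every analysis in section 3.11 succeeded, the study would have a risk marker. A report that followed the objectives as worded would present it as a criterion for selecting patients for CRT, which those analyses would not support.

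**Working it through.** **1. Does any stated analysis contain treatment?** The protocol gives no figure for treatment response to reproduce, so the check is a reading of each method.

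- *ANOVA (3.11):* the grouping factor is deteriorated v unchanged. No treatment factor.
- *ROC (3.11):* cut-offs, sensitivity and specificity. No treatment.
- *Logistic regression (3.11):* predictors of admission, then of death or transplantation. No treatment term, stratum or marker-by-treatment term is named.
- *Clustering (3.9):* the named inputs are clinical parameters, LV volume, wall stress and deformation traces. Treatment is not named. Even as an input it would help to group patients; it would not yield a treatment effect.
- *Power (3.10):* a strain difference between outcome groups, and a relative risk of 1.8 for a marker. Both concern association with outcome.

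**2. What risk prediction leaves open (assumed numbers, not from the protocol).** Let untreated risk be 40% in marker-positive and 20% in marker-negative patients, so the relative risk is 0.40/0.20 = 2. Absolute benefit = untreated risk × (1 − relative risk under CRT).

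- *Case A, CRT relative risk 0.7 in both groups:* 0.40 × 0.3 = 12 points v 0.20 × 0.3 = 6 points.
- *Case B, CRT relative risk 1.0 in marker-positive and 0.5 in marker-negative patients:* 0.40 × 0 = 0 points v 0.20 × 0.5 = 10 points.

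The untreated relative risk is 2 in both cases. It does not show which group gains more.

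**3. The same cases with CRT and non-CRT patients pooled.** The protocol does not restrict its analyses to untreated patients. Assume that 30% of each marker group have CRT.

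- *Case A:* treated risks are 0.40 × 0.7 = 28% and 0.20 × 0.7 = 14%. Pooled: 0.7 × 40 + 0.3 × 28 = 36.4% v 0.7 × 20 + 0.3 × 14 = 18.2%. Relative risk 36.4/18.2 = 2.00.
- *Case B:* treated risks are 40% and 20 × 0.5 = 10%. Pooled: 40% v 0.7 × 20 + 0.3 × 10 = 17%. Relative risk 40/17 = 2.35.

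The pooled marker looks stronger in the case where marker-positive patients gain nothing. A strong pooled association is therefore no evidence of benefit.

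**4. What a direct test would need (assumed inputs).** For a marker-by-treatment interaction, events = (1.96 + 0.8416)² / [q(1−q) × m(1−m) × (ln R)²]. Here q is the share treated, m = 0.5 the marker prevalence, R = 1.8 the ratio of hazard ratios, with two-sided alpha 0.05 and 80% power. The numerator is 7.849 and (ln 1.8)² = 0.3455.

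- q = 0.5: 7.849 / (0.25 × 0.25 × 0.3455) = 364 events
- q = 0.3: 7.849 / (0.21 × 0.25 × 0.3455) = 433 events
- q = 0.2: 7.849 / (0.16 × 0.25 × 0.3455) = 568 events
- q = 0.1: 7.849 / (0.09 × 0.25 × 0.3455) = 1010 events

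A marker main effect of hazard ratio 1.8 with m = 0.5 needs 7.849 / (0.25 × 0.3455) = 91 events. The interaction needs 4 to 11 times as many. At 10% treated, the number of events exceeds the planned minimum of 1000 patients. These counts take no account of confounding.

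**The case against.** The strongest reply is that treatment is in the protocol and the claims are cautious. Section 3.6 provides a pre-implant baseline for CRT patients, section 3.1 collects medication and device history, and secondary objective 5 compares types of pacing. Secondary objective 3 sets out to compare risk with response indicators, so it tests secondary hypothesis 3 and does not assume it. Its model may stand in a statistical analysis plan that was not available here. Section 1 calls risk identification a step before randomised CRT trials, and the wording on patient selection in sections 2.1, 2.2 and 4.2 is hedged.

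Most of this stands. It would be wrong to say that treatment is absent from the protocol, or to fault it for not printing the model for secondary objective 3. But a later model would not remove confounding by indication, because treatment is not allocated. Nor can it make eligibility follow from risk prediction in primary objective 1, which is not hedged.

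A reader might also infer that the protocol's own background shows risk and response running in opposite directions. Section 1.5 links absence of the typical pattern to worse outcome after CRT, and section 1.6 says: "The mismatch between ECG and myocardial mechanics was independently associated with increased risk of adverse outcome". The documents do not support that inference. These are results in patients implanted with or selected for CRT, and they say nothing about untreated risk. Secondary hypotheses 1 and 4 point the other way: they link dyssynchrony to earlier decline, and absence of the classic pattern with sustained work under stress to good prognosis. Section 1.5 links typical patterns to CRT response. Markers of risk and of response may well coincide in this population. The point is that the stated analyses do not test it.

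**Conclusion.** The concern holds for the conclusions claimed, not for the prognostic work. As stated, the analyses can show whether strain pattern, myocardial work and AI-derived groups predict outcome. They cannot show who benefits from CRT or medication. This affects primary objectives 1 and 2, primary hypotheses 1 and 2, and secondary hypothesis and objective 3.

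The protocol gives no figure from which to size the error. The 40%/20% cases and the event counts rest on assumed risks, treated shares, marker prevalence and effect ratio. They show that risk does not determine benefit and that an interaction would be imprecise. They do not show that the study's conclusion would be reversed.

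It should be corrected, but it is not fatal: no sample, measurement or prognostic analysis becomes invalid.

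**What to change.** 1. Reword primary objectives 1 and 2 and primary hypotheses 1 and 2 as risk prediction. Objective 1 could ask whether echocardiographic myocardial work predicts outcomes a) to d) in LBBB. Remove CRT eligibility and treatment response as conclusions. This agrees with section 1, which places risk identification before randomised CRT trials.
2. Keep secondary hypothesis 3 and secondary objective 3 only as exploratory and hypothesis-generating.
3. Report prognostic results separately for patients with and without CRT.
4. Call change in treated patients 'change after CRT', not response, since it includes the natural course.
5. Label any marker-by-CRT comparison as low in precision and open to confounding by indication. This holds even after adjustment for EF, QRS length, LBBB morphology and NYHA class, which section 1.6 names as the basis of CRT management. Section 1.4 says that guidelines assign CRT only in established heart failure, so treated and untreated patients may overlap little.

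**Cost.** A few sentences in sections 2.1 to 2.4, and a split of results on data already to be collected. The study's claim becomes more modest, and the separate CRT results will be less precise than pooled ones.

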### 2.4 Secondary objectives:

1. To investigate the dependency of strain-patterns on afterload and ventricular geometry
2. To investigate the predictive value of repeated echocardiographic measures after one year
3. To compare indicators for increased morbidity and mortality risk with indicators for CRT or medical treatment response
4. To assess development of strain-patterns for dyssynchrony, ventricular volume and clinical and echocardiographic parameters for systolic function over time in dependency on myocardial work during stress testing
5. To compare outcomes between usual ventricular pacing and HBP.

## 3 Project arrangements, method selection and analyses

### 3.1 Patients

This is a longitudinal prospective cohort-study intending to include at least 1000 patients with LBBB from University Hospital of North Norway Tromsø and Harstad, Akershus University Hospital, Lørenskog, Oslo University Hospital, Rikshospitalet, Haukeland University Hospital, Bergen and Nordlands Hospital, Bodø, over a 2-year inclusion period.

Information about present and previous diseases, medication, surgical- or invasive treatment, PM, ICD or CRT implantation, clinical examination and present and previous echocardiographic imaging and blood samples (Hb, Thrombocytes, CRP, Kreatinine, eGFR, Urate, HbA1C, Cholesterol, ProBNP, Troponins, ALAT and Ferritin) will be accessed by the patient's journal.

All prospective study participants will answer one customized and two standardized (EQ5D and HeartQoL) questionnaires. They will undergo general clinical investigation comprising height and weight measurements, baseline ECG, blood samples when not found in the patient's journal, standardized BP measurements and echocardiography with a 3 minutes- hand-grip test at baseline and in a 18 month follow-up study.

Clinical outcome data including death and hospital admissions due to heart failure and CRT implantation will be assessed after 3 and 5 years (eventually after 10 and 15 years) by linkage to data from the patient's clinical records through access to Norwegian Patient Registry (Norsk pasientregister (NPR)), Norwegian Causes of Death Registry (Dødsårsaksregisteret) and Norwegian Cardiovascular Disease Registry (Hjerte- og karregisteret).

St Olavs Hospital, Trondheim, might provide retrospective patient data with echocardiography loops, where outcome-data will be extracted from the same registries.

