This study will include prospectively clinical patients from the cardiological outpatients' clinics, and the cardiology wards in University Hospital of North Norway Tromsø and Harstad, Akershus University Hospital, Lørenskog, Oslo University Hospital, Rikshospitalet, Haukeland University Hospital, Bergen and Nordlands Hospital, Bodø. Furthermore, we intend to use retrospectively collected data of population-based study from the Katholieke Universiteit (KU) Leuven, Belgium and invite participants with LBBB or predominant ventricular pacing (PVP) from the Tromsø 7 study for the prospective study. The study is furthermore open to include retrospectively datasets where subjects with LBBB or PVP can be identified and echocardiographies are taken (e.g. St. Olav Hospital, Trondheim). Prospectively included patients will be followed by a repeated echocardiography study after one year and access to patient registries through 5 years (eventually up to 15 years). All studies abroad will follow their own study protocol and follow-up.

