### 3.4 Primary outcome

Deterioration, stability or improvement of markers for myocardial function over time. Outcome-variables will be measured by deterioration or non-deterioration of LV function by defining deterioration of ventricular function by using either echocardiographic parameters that are classically used for the definition of CRT responders: EF decrease by >5% with EF initially <55% or >10% with EF initially  $\geq$  55%, LV diastolic or systolic volume enlargement by 10%, NYHA class deterioration or proBNP increase by >10%.

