### 3.10 Statistical power

It is unknown how high the percentage in this study population will be who suffer from deterioration of LV function. Therefore, a pilot-study on the first 100 study-subject of the different subgroups will be performed in order to calculate the power of the final population size. Pilot participants will be included into the final study population. Assuming different proportions of 5%, 10%, 20% and 30% of patients with deteriorating ventricular function, a difference in septal or global strain between at 5% at a SD of  $\pm 6\%$  the sample size needed for hypothesis 1 in each subgroup will be 220, 129, 73 or 57, respectively for a two-sided test and a Type I error of 0.05.

For calculation of hazard-ratios between patients with against without deterioration of LV function for the primary outcome variable: hospital admission due to CVD, assumed that 5% of all patients either

deteriorate function and the presence of decreased segmental work indicates at least a relative risk of 1.8, at an alpha of 0.05 with 500 patients included, the statistical power will be 82%.

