### 3.12 Data management

Data from patient's visit and patient's journal will be stored as de-identified data in an a password secured internet-based database (Viedoc). Viedoc is approved by The Norwegian Data Protection Authority for use in scientific studies. Echocardiographic data will be stored as de-identified DICOM files including locally performed measurements, labeled by the patient's study ID, all ECGs will be taken in digitalized format and be stored as de-identified image files as well as DICOM files. All de-identified files will be locally stored at a dedicated server. Key files coupling personal patient information to ID's will be stored locally on a server with restricted access. All de-identified ECGs, echocardiography-studies and key-files will be centrally collected at University Hospital of North Norway, Tromsø, latest after end of the second patient's visit. Echocardiographic data will be analyzed in the core-lab at University Hospital of North Norway, Tromsø. Readers of the strain-data will be blinded for the outcome-data. Other researchers assess outcome-data from NPR and The Norwegian Cause of Death Registry will be added to the database. The de-identified dataset and DICOM images from echocardiography and ECG will also be transferred to NTNU Trondheim for automated reading of the echocardiographic imaging and AI purposes.

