## 4 Plan for activities, visibility and dissemination

Data collection will start after final Regional Ethics Committee (REK) and Data Protection Officer (PVO) approval. A long-term follow-up of at least 5 years, possibly 10 to 15 years is planned after an inclusion period of at least 2 years plus one-year clinical control. A core-lab will be established in Tromsø for analyses of all echocardiographic measurements and post-processing. University Hospital of North Norway, Tromsø will coordinate and assess the quality of data acquisition and database from the different centers. All registry-data from NPR and The Norwegian Causes of Death Registry as follow-up data will be retrieved by a dedicated research administrator.

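### The repeat echocardiography that defines deterioration is set at 18 months in 3.1 but at one year elsewhere, and the primary outcome in 3.4 gives no time

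*Protocol*

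**What the plan says.** Five sections of the protocol bear on when the repeat assessment takes place.

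- Section 3.1, which sets out what is done at each visit, has "echocardiography with a 3 minutes- hand-grip test at baseline and in a 18 month follow-up study".
- Section 1 says that prospectively included patients "will be followed by a repeated echocardiography study after one year", with registry access thereafter.
- Section 2.4, second secondary objective, concerns the "predictive value of repeated echocardiographic measures after one year".
- Section 3.11 compares patients with deteriorating myocardial function with "those with unchanged clinical condition after one year".
- Section 4 places long-term follow-up "after an inclusion period of at least 2 years plus one-year clinical control".

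Section 3.4 defines the primary outcome as "Deterioration, stability or improvement of markers for myocardial function over time" and gives thresholds for EF, LV volume, NYHA class and proBNP, but no time point. Section 3.12 has the de-identified recordings collected centrally "latest after end of the second patient's visit".

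On study size, section 3.10 states "It is unknown how high the percentage in this study population will be who suffer from deterioration of LV function". It works through proportions of 5%, 10%, 20% and 30%, and leaves the final size to a pilot in the first 100 patients (also described in 3.7). Neither the proportions nor the pilot rate is given an interval.

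**The concern.** The primary outcome is a change between two assessments, so the interval is part of its definition. EF and LV volume change in particular can only be read at the repeat echocardiogram. If that examination takes place at 18 months, as in 3.1, the one-year comparison in 3.11 has no matching echocardiogram. If it takes place at one year, 3.1 instructs the sites wrongly.

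Several hospitals recruit. A site working from 3.1 and a site working from section 1 would examine patients six months apart, and both would be following the protocol. Interval would then be mixed up with centre in the comparison of deteriorating and stable patients.

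The sizing has the same problem. A pilot deterioration rate can only be set against the 5% to 30% scenarios if both refer to the same length of follow-up.

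**Working it through.** **Step 1: the sections side by side.**

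| Protocol section | What is timed | Time |
|---|---|---|
| 3.1 | Repeat echocardiography with hand-grip test | 18 months |
| 1 | Repeat echocardiography | one year |
| 2.4 | Repeat echocardiographic measures | one year |
| 3.11 | Comparison of deteriorating and unchanged patients | one year |
| 4 | Clinical control after inclusion | one year |
| 3.4 | Primary outcome | none given |
| 3.7, 3.10 | Pilot rate; assumed proportions | none given |

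One section says 18 months and four say one year. Section 4 is the weakest of the four because it does not mention echocardiography.

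**Step 2: could there be two follow-up visits?** No section describes both a 12-month and an 18-month visit. Section 1 describes one repeat echocardiogram and then registries. Section 3.12 ties data collection to a second visit, which fits baseline plus one repeat. A single repeat visit is an inference, but the only one the text supports. Had two been intended, the protocol would still need to say which one defines the outcome.

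**Step 3: size of the discrepancy.** 18 − 12 = 6 months, and 6/12 = 50% of the shorter interval. With the two-year inclusion period of 3.1, the last repeat visit falls at 24 + 12 = 36 months or 24 + 18 = 42 months from the start. Section 4 speaks of a minimum inclusion period, so both are earliest dates; the 6-month gap is the same either way.

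**Step 4: illustration of the effect on the 3.10 proportions.** The protocol does not say how deterioration accumulates, so this needs an assumption.

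- If threshold crossings do not accumulate, the proportions are the same at both times.
- If they accumulate at a constant rate, a 12-month proportion p becomes 1 − (1 − p)^1.5 at 18 months, and an 18-month proportion p corresponds to 1 − (1 − p)^(2/3) at 12 months.

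| Proportion in 3.10 | If it is a 12-month figure, value at 18 months | If it is an 18-month figure, value at 12 months |
|---|---|---|
| 5% | 7.4% | 3.4% |
| 10% | 14.6% | 6.8% |
| 20% | 28.4% | 13.8% |
| 30% | 41.4% | 21.2% |

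**Step 5: what that would do to the subgroup sizes.** Section 3.10 uses a strain difference of 5 with SD 6 and two-sided alpha 0.05. It states no power for this calculation, so 80% is assumed here. The normal approximation is N = [6 × (1.960 + 0.842)/5]² / [p(1 − p)] = 11.3 / [p(1 − p)].

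For 5%, 10%, 20% and 30% this gives 238, 126, 71 and 54, against the stated 220, 129, 73 and 57. The last three rows agree closely; the 5% row does not, which is a separate matter. With the converted proportions:

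- if 3.10 gives 12-month figures and the visit is at 18 months: 165, 91, 56 and 47;
- if 3.10 gives 18-month figures and the visit is at 12 months: 348, 179, 95 and 68.

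The finding rests on steps 1 and 2. Steps 4 and 5 only show how far the sizing could move.

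**The case against.** The strongest reply is that the conflict is narrow. Section 3.4 gives the thresholds and 3.11 supplies an analysis time of one year for the same construct, so 3.1 may simply be the odd one out. That may well be so, but the document does not say it, and 3.1 is the section a site would use to book visits. A statistical analysis plan can choose an analysis time; it cannot decide after the fact when the examination was done.

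A second reply is that the pilot will replace the scenarios. Pilot patients join the final cohort, so their rate can be measured at whatever interval the study uses. Also, six of the eight converted values in the table still lie within 5% to 30%. This reduces the consequence for sizing but does not remove it: the pilot rate needs a stated interval before it can be used.

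A third is that the constant-rate model is an outside assumption. The outcome is read at one visit and can improve as well as worsen. That is right, and the figures are offered only as an illustration whose lower end is no change.

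Finally, a visit window and adjustment for the actual interval are details that may sit in an analysis plan not shown here. Their absence is not the fault. The fault is that the protocol states two different visit times.

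**Conclusion.** The concern holds. The protocol places the same repeat assessment at 18 months in 3.1 and at one year in 1, 2.4 and 3.11, with support from section 4, and nothing reconciles them. The contradiction falls on the primary outcome in 3.4 and carries through to the pilot-based sizing in 3.7 and 3.10.

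Its certain size is six months in the measurement interval, and six months in the earliest date of the last repeat visit (36 or 42 months with two-year inclusion). The effect on the proportions deteriorating runs from none to the constant-rate values tabulated above. The conclusion assumes one repeat visit, as the text indicates.

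This should be corrected, but it does not invalidate the study: the registry outcomes at 3 and 5 years do not depend on it. The document does not show which interval is intended, and this review does not choose between them.

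**What to change.** 1. Reconcile sections 1, 2.4, 3.1, 3.11 and 4 to one repeat-visit time with a window, and state that time in 3.4 as part of the primary outcome definition.
2. Tie the 5% to 30% proportions in 3.10, and the pilot deterioration rate in 3.7 and 3.10, to the same interval.
3. Record each patient's actual baseline-to-repeat interval. If visits fall at differing intervals, adjust for it in the deterioration analysis; the details can go in the analysis plan. This step remains useful even if some visits have already taken place.

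The cost is protocol wording and one recorded interval per patient. No new visit is needed.
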